7.2 PARTICIPANT DISCONTINUATION/WITHDRAWAL FROM THE STUDY

Participants are free to withdraw from participation in the study at any time upon request.

An investigator may discontinue or withdraw a participant from the study for the following reasons:

- If the participant meets an exclusion criterion that precludes further study participation.

The reason for participant discontinuation or withdrawal from the study will be recorded on the study REDCap. Subjects from the dialysis center randomized to initial SPIRIT who sign the informed consent form but do not receive the study intervention may be replaced. Subjects in the initial SPIRIT who sign the informed consent form and receive the study intervention, and subsequently withdraw, or are withdrawn or discontinued from the study will not be replaced.

7.3 LOST TO FOLLOW-UP

Patients lost to follow-up will not be applicable in this trial since all patients must come to the dialysis center for their treatment and thus can be contacted at the center.

A surrogate participant will be considered lost to follow-up if he or she fails to complete the scheduled 2-week follow-up (after the receipt of the intervention) and is unable to be contacted by the study site staff until the end of the 9-month follow-up period. Or, a surrogate participant will be considered lost to follow-up if he or she fails

to complete the scheduled 3-month follow-up (after the patient's death) and is unable to be contacted by the study site staff.

The following actions must be taken if a participant is determined to be lost to follow-up:

- The site will attempt to contact the participant and reschedule the missed appointment for 4 weeks and ascertain if the participant wishes to continue in the study.
- Before a participant is deemed lost to follow-up, the investigator or designee will make every effort to regain contact with the participant (where possible, 3 telephone calls and, if necessary, a certified letter to the participant's last known mailing address or local equivalent methods, or speak to the patient at the dialysis center). These contact attempts will be documented in the participant's record in REDCap.
- Should the participant continue to be unreachable, he or she will be considered to have withdrawn from the study with a primary reason of lost to follow-up.

8 STUDY ASSESSMENTS AND PROCEDURES

8.1 OUTCOME ASSESSMENTS

Collecting effectiveness outcome data will be centralized; research staff at the Study Coordinating Center will collect the data from patients and surrogates by phone. Telephone-based collection minimizes participants' travel burden. Centralized data collection maintains data collectors being blind to group assignment. The preparedness outcomes will be assessed at 2 weeks post-intervention, as in our R21 trial.¹⁸ We expect roughly 40% of study patients (~160) to die by the 9-month follow-up; deaths are readily identifiable through dialysis clinics and will trigger post-bereavement surveys with surrogates at 3 months and staggered CMS data collection. Post-bereavement assessment at 3 months is based on our efficacy data showing that distress symptoms sharply rose in both groups 2-weeks post-bereavement and then stabilized at 3 months.

Effectiveness Outcomes

Preparedness for end-of-life decision making (measured at baseline and 2 wks post-Session II):

- **Dyad congruence** will be assessed using the Goals-of-Care Tool,^{18,20} which includes two scenarios describing medical conditions commonly occurring in ESRD patients. In the first, the patient develops a severe complication and cannot speak for himself/herself; the medical team believed recovery unlikely and continuing life-sustaining treatment, including dialysis, would no longer be beneficial. In the second scenario, the patient develops advanced dementia. Each scenario has three response options: "The goals of care should focus on delaying my death, and thus I want to continue life-sustaining treatment", "The goals of care should focus on my comfort and peace, and thus I do not want life-sustaining treatment, including dialysis", and "I am not sure". Patients and surrogates complete this tool independently and their responses are then compared to determine dyad congruence -- either congruent in both scenarios or incongruent. If both members of the dyad endorse "I am not sure", they are considered incongruent.
- **Patient decisional conflict** will be measured using the 13-item Decisional Conflict Scale (DCS), a validated measure in the context of end-of-life decision making¹⁷; higher scores indicate greater difficulty in weighing benefits and burdens of life-sustaining treatments and decision making (range 1-5; Cronbach's $\alpha = 0.8 - .93^{17,18,20,72}$).
- **Surrogate decision-making confidence** will be measured using the 5-item Decision Making Confidence (DMC) scale (Cronbach's $\alpha = 0.81-0.90^{18,34}$) on which higher scores reflect greater comfort in performing as a surrogate (range 0, not confident at all-4, very confident). DMC is a self-report of a surrogate's confidence in: knowledge of the patient's wishes, ability to make treatment decisions even in a highly stressful situation, ability to seek information about risks and benefits of medical choices, ability to handle unwanted pressure from others, and ability to communicate with health care providers about the patient's wishes.

- **Composite outcome:** We will also create a composite outcome combining dyad congruence and surrogate DMC to differentiate surrogates who understand the patient's wishes and feel confident in their role from those who don't (understand the wishes but lack confidence, misunderstand the wishes but feel confident, neither understand nor feel confident).^{18,34}
- We will also assess the **overall preparedness for end-of-life decision making** using the 26-item investigator-developed measure. The measure assesses the level of preparedness for end-of-life decision making in the cognitive, emotional, and behavioral dimensions on a 4-point scale (4=strongly agree to 1=strongly disagree) with higher scores indicating higher levels of preparedness. Patient and surrogate each will complete this measure separately.

During the supplement cohort study, the participating dyads will complete the same measures above twice, at enrollment and 6 months after.

In addition, they will complete the COVID-19 Stress Scale. **COVID-19 Stress Scale**³⁵ is a 35-item measure to assess pandemic related emotional responses (i.e., COVID-19 stress and anxiety symptoms) on a 5-point scale ranging from 0 (not at all) to 4 (extremely). The subscales are (1) danger and contamination fears, (2) fears about economic consequences, (3) xenophobia, (4) compulsive checking and reassurance seeking, and (5) traumatic stress symptoms about COVID-19. The scale has demonstrated excellent internal consistency reliability (Cronbach's $\alpha > .8$ for all subscales) and convergent and discriminant validity. We will also add an overall rating to assess how much respondents worry about COVID-19, which recently was used by Wang *et al.*,³⁶ "Please rate the level of your current worry toward COVID-19" on a scale ranging from 1 (very mild) to 10 (very severe).

Surrogates' post-bereavement psychological distress (at baseline and 3 mo. post patient death):

Symptoms of anxiety, depression, and post-traumatic distress^{42,73} will be measured using the Hospital Anxiety and Depression Scale (HADS)⁷⁴; subscale scores range from 0 to 21 with higher scores indicating greater symptom severity. Internal consistencies and test-retest reliabilities are 0.88–0.90 and 0.84–0.94, respectively.⁷⁵ Intensity of post-traumatic distress symptoms will be assessed using the Post-Traumatic Symptoms Scale-10 (PTSS-10).⁷⁶ Higher scores indicate more intense symptoms (range 10–70).⁷⁷ The PTSS-10 has been shown to have high sensitivity and specificity.^{76,78,79}

Implementation Process Outcomes

For the **initial SPIRIT intervention**, after the final dyads have completed the SPIRIT sessions (~Year 3, Q1), care providers will complete a survey and an interview.

- **Care provider acceptability** will be evaluated using the 7-item Care Providers' Perceived Acceptability Survey to assess their perceptions about SPIRIT implementation, including the time required, impact on interactions with patients, and whether they would recommend SPIRIT to other clinics.⁸⁰ Response options range from 1=strongly disagree to 4=strongly agree; higher scores indicate greater acceptability.
- **A brief (~15 min.) semi-structured interviews (face-to-face or by telephone; audio-recorded) will obtain providers' perspectives** on whether the implementation of SPIRIT is compatible with their setting and the workflow, its perceived utility, their willingness to continue using it after the study, factors influencing implementation (barriers, logistical constraints, and facilitators), and suggestions for improvement.
- **Patient and surrogate acceptability** will be assessed using the 10-item ACP Acceptability Questionnaire developed from our previous trial.²⁴ Participants are asked how strongly they agree or disagree (4 to 1) with statements about their experience with SPIRIT sessions, including duration, interactions with the care provider, level of comfort and satisfaction. Higher scores indicate greater acceptability. Each patient and surrogate will complete this survey at the 2-week post-intervention follow-up.
- **Fidelity/adherence** will be assessed using two independent data sources, (a) the SPIRIT Interview Guide, Checklist, and self-evaluation completed by the care provider after each SPIRIT session and (b) patient and surrogate responses to the SPIRIT components coverage during the 2-week post-intervention follow-up as described above. The number of SPIRIT components covered, the minutes required for the care provider

to complete the sessions, the number of dyads who complete SPIRIT sessions, and the number of incomplete or interrupted sessions will be aggregated.

- **Intervention costs** will be estimated based on the actual time the care provider spent in carrying out SPIRIT, multiplied by hourly wage (+benefits), plus costs of materials. Overhead (e.g., facility) costs and research staff's time will not be included.
- We define **sustainability** as the extent to which a newly implemented intervention is maintained within a service setting's ongoing, stable operations.⁸¹ In Y4, Q4, we will conduct a brief interview with SPIRIT care providers to ask about sustainability: (a) Is SPIRIT on-going (and at what frequency)? (b) What components of the SPIRIT protocol have been retained? and (c) Has SPIRIT implementation been evaluated at the clinic level? If so, how?⁸²

For the delayed SPIRIT implementation, the process evaluation will involve care providers only since patient and surrogate study participation will have ended at the end of 9-month follow-up or patient death. Care provider acceptability, fidelity, and intervention costs will be determined as described above.

End-of-life treatment intensity (upon patient death)

We will link study data to publicly available USRDS data. The USRDS captures inpatient and outpatient Medicare claims on all treated U.S. ESRD patients and releases these data annually free of charge. Medicare claims data are the most complete and reliable source of data on end-of-life care intensity because patients on dialysis are Medicare beneficiaries. The USRDS data are far superior to that which could be obtained through individual hospitals because data collection at the latter is extremely difficult and highly likely to result in missing data. From the inpatient and outpatient claims data, we will obtain dates and attributed causes of death; dates of hospital, skilled nursing facility, and hospice admissions and discharges; dates of outpatient encounters (including dialysis sessions and ED visits); and diagnostic and procedure codes for all inpatient and outpatient encounters. Thus, we will be able to determine hospitalization, ICU days, days hospitalized, use of intensive procedure, (dis)continuation of dialysis (also from CMS Form 2746), and hospice use during the final month of life. We will consider the following to be intensive procedures: mechanical ventilation, feeding tube placement, dialysis, and cardiopulmonary resuscitation.²² These intensive procedures will be identified using HCPCS and ICD-9-CM codes (e.g., ICD-9 codes for intubation and mechanical ventilation: 96.04, 96.05, 96.7X).⁸³

Descriptors and Potential Covariates

- Patients and surrogates will complete a **Sociodemographic Profile** which includes age, gender, race and ethnicity, type of relationship between patient and surrogate, marital status, religious affiliation, education, household income, previous end-of-life decision-making experience, and previous participation in an ACP discussion or AD completion.
- To describe the sample, **the patient's clinical characteristics**, including dialysis modality, years on dialysis, comorbid conditions will be abstracted from the patient's EMR.
- **Care providers' sociodemographic data** will include age, gender, race and ethnicity, education, and years of practice.
- At baseline, we will collect **clinic-level contextual data**⁸⁴ that could facilitate understanding study results, including staffing, patient census, rural-urban status,⁸⁵⁻⁸⁹ palliative care and hospice availability, and proximity of hospitals.

For Supplement Aims,

- **The preparedness outcomes measures** will be assessed at baseline and 2-3 days after the intervention.
- **Surrogates' post-bereavement psychological distress** will be assessed using the HADS, which will be completed at baseline and 1 month post patient death.
- **Patients' level of articulation of end-of-life wishes:** Using a "quantitizing" technique of qualitative data analysis,³⁹ two raters will independently review SPIRIT session transcripts focusing on the values of

treatment outcomes and the goals of care discussions and rate the level of patient's articulation of end-of-life care preferences on a 3-point scale (3=expressed wishes very coherently, 2=somewhat coherently, 1=unable to express wishes coherently). Inter-rater reliability (percent agreement) will be established, targeting $\geq 90\%$.

- **Care decisions (assessed at 6 months post intervention or after the patient's death, whichever occurs first):** Stopping dialysis, DNR order, and hospice enrollment are major care decisions that must involve the treating physician (or APRN) and social worker. These decisions are also required to be documented in the CMS Form 2746 in the event of a dialysis patient's death. On a monthly basis, the research coordinator will check in with the outpatient dialysis APRN to track these care decisions and will be aggregated at 6 months.
- **Descriptors and Potential Covariates (collected at baseline):** Patients and surrogates will each complete a Sociodemographic Profile which includes demographic information and previous end-of-life decision-making experience. Patients' clinical characteristics (e.g., date of dementia diagnosis, etiology of dementia, and comorbid conditions) will be abstracted from the patient's medical records.

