1.2 SCHEMA

1.3 SCHEDULE OF ACTIVITIES (SOA): Randomization occurs at the clinic level

Days offset	Procedure	Note
Patients and surrogates	Patient referrals ^a	Screened and willing patients
	Patient screened (by research staff) ^b	Linked to eligibility checklist
Day -14 to Day -7	Obtaining patient informed consent in person ^b	Scan and upload signed consent pdf
	Obtaining contact information ^b	
	Medical record review: clinical characteristics ^b	To be linked to "pt consent"
	Usual care review 1 ^b	To be linked to "pt consent" & separate Every 6 months
Day 0	Surrogate verbal consent ^b	
	Surrogate verbal consent received ^b	
	Scheduling baseline (T1) appointment	If control, schedule both T1 & T2
	Reminder call for T1	
Day 14 (+/- 7)	Baseline (T1)-patient completion	Link to the measures
	Baseline (T1)-surrogate completion	Link to the measures
	Payment (T1) mailed to patient	With thank-you note
	Payment (T1) mailed to surrogate	With thank-you note
	Scheduling SPIRIT Session I & II and 2-wk F/U ^b	Need to coordinate with the care provider for SPIRIT sessions
	SPIRIT Session I^a	
	SPIRIT Session II reminder call ^b	Two days prior
	SPIRIT Session II^a	
	SPIRIT Interview Guide Checklist ^b	Care provider interventionist completes and the Site Coordinator enters to REDCap
	Reminder call for T2	Central
	2-week follow-up (T2)-patient completion	2 weeks from SPIRIT; including acceptability survey and SPIRIT components
	2-week follow-up (T2)-surrogate completion	2 weeks from SPIRIT; including acceptability survey and SPIRIT components
	Payment (T2) mailed to patient	With thank-you note
	Payment (T2) mailed to surrogate	With thank-you note
	Monthly check-in call 1	1 month from T2
	Monthly check-in call 2	
	Monthly check-in call 3	
	Monthly check-in call 4	
	Monthly check-in call 5	
	Usual care review 2 ^a	May need one more
	Monthly check-in call 6	
	Monthly check-in call 7	
	Monthly check-in call 8	
	Monthly check-in call 9	With note on study completion
	Mailing sympathy card	Upon patient death
	Contacting surrogate & scheduling a 3-month post-death F/U	
	Postcard reminder 2 weeks before the F/U	
	Reminder call for 3-month F/U	
	F/U 3 month post death	
	Payment (F/U 3M) mailed to surrogate	With thank-you note
	Clinic-level contextual data ^b	At the end of each implementation
Care providers	Informed consent ^b	At the end of each implementation
	Acceptability assessment^b	Brief survey and interview
	SPIRIT care provider interview-sustainability^b	

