Care provider acceptability	Dialysis care provider's perceived acceptability (range, 7-28); Semi-structured interview			✓	End of the initial implementation
Patient & surrogate acceptability	Patient and surrogate acceptability (range, 10-40 each)	✓	✓		2 wks
Fidelity	SPIRIT provider's coverage of the SPIRIT components and durations; Brief patient and surrogate survey	✓	✓	✓	SPIRIT provider after each SPIRIT completion Patient and surrogate at 2 wks
Intervention costs	The actual time the care provider spent in carrying out SPIRIT, multiplied by hourly wage (+benefits), plus costs of materials				End of the early implementation
Sustainability	Brief semi-structured interview		✓		End of 12 mo. post 9-month follow-up
Delayed implementation process evaluation					
Care provider acceptability	Dialysis care provider's perceived acceptability (range, 7-28); Semi-structured interview			✓	End of the delayed implementation
Fidelity	SPIRIT provider's coverage of the SPIRIT components durations			✓	SPIRIT provider after each SPIRIT completion
Intervention costs	The actual time the care provider spent in carrying out SPIRIT, multiplied by hourly wage (+benefits), plus costs of materials				End of the delayed implementation
Descriptors and potential covariates					
Sociodemographics	Sociodemographic Profile	✓	✓		Baseline for patients and surrogates
				✓	End of the initial implementation for clinicians
Clinical characteristics	Medical Profile				Baseline
Clinic-level contextual data	Contextual Data Collection Form				End of each implementation
Usual care	Documented AD completion on the Plan of Care form; presence of DNR, POLST, or MOST (from EMR)				Baseline and 6 mo.

Pt, patient; Srgt, surrogate; Pro, care provider

[figure not shown]
Data collection highlighted in yellow is performed locally.

For supplement aims:**Measurement and data collection time points**

Outcome	Measure	Completed by		Time points
		pt	srgt	
Estimating the effects of SPIRIT-dementia				
Preparedness				
Dyad congruence	Goals-of-Care Tool (2 end-of-life scenarios)	✓	✓	Baseline and 2-3 days
Patient decisional conflict	Decisional Conflict Scale (range, 1-5)	✓		Baseline and 2-3 days
Surrogate decision-making confidence	Decision Making Confidence Scale (range, 0-4)		✓	Baseline and 2-3 days
Overall preparedness	Preparedness for End-of-Life Decision Making (range, 26-104)	✓	✓	Baseline and 2-3 days
Post-bereavement distress	HADS (each subscale range, 0-21)		✓	Baseline and 1 mo. after patient death

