6.2 PREPARATION/HANDLING/STORAGE/ACCOUNTABILITY

6.2.1 INTERVENTIONIST TRAINING AND ACCOUNTABILITY

Care Provider Training for SPIRIT

The ideal individual to conduct ACP discussions is still unknown, but we believe it is not the profession per se but rather the willingness and appropriate training that make an individual suitable for conducting the discussions. Each dialysis clinic has identified a care provider designated to conduct SPIRIT sessions (e.g., ANP, RN, MSW). SPIRIT training will occur shortly after randomization for the initial implementation clinics and in early Year 4 for

the delayed implementation clinics. The SPIRIT trainers, trained and certified by the PI at the Study Coordination Center (at Emory), will conduct SPIRIT training for all four sites based on the manualized curriculum.

Care provider training will consist of a 1½-day, competency based program that has been used in our previous trials:

- Module 1 (1/2 day) to ensure understanding of end-of-life care issues and communication as key to improving end-of-life care and the Representational Approach (theoretical underpinnings of SPIRIT);
- Module 2 (1/2 day), as skill-base session to gain understanding of the SPIRIT intervention and delivery, including role plays. A 2-week practice period will be scheduled for integration of skills and exploration of additional learning needs; and
- Module 3 (1/2 day) for skill-demonstration and certification. These training sessions will be conducted in collaboration with the Emory Nursing Professional Development Center.

For Supplement Aims:

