9.4.3 ANALYSIS OF THE SECONDARY ENDPOINT(S)

Analysis of secondary endpoints are not dependent on findings of primary endpoints.

SPIRIT effectiveness on surrogates’ post-bereavement psychological distress: We will use the same approach as in the analysis of the primary endpoints to compare anxiety, depression, and post-traumatic distress symptoms in SPIRIT vs usual care among surrogates of patients who die during the initial implementation and 9-month (or extended) follow-up.

Implementation process outcomes: Quantitative data on acceptability, fidelity, and costs of SPIRIT will be summarized using descriptive statistics. SPIRIT will be determined to be acceptable to care providers and patients and surrogates if over 75% of responses exceed an average summative score ≥ 3 (of 4) on the acceptability measures. Cost estimates will be used to ascertain resources needed to implement or replicate SPIRIT in the

future.⁹² We will also explore the relationships of these quantitative data with characteristics of settings and stakeholders. Transcripts of acceptability interviews will be transferred to ATLAS.ti for analysis. Content analysis techniques⁹³ will be used without preconceived categories.⁹⁴ Open coding will be applied⁹⁵ and disagreements on coding will be resolved by consensus. We will examine the data for patterns or differences in themes between those with acceptability scores ≥ 3 and scores < 3 and setting characteristics. This analysis will be facilitated by creating matrixes that organize textual and numeric data for comparing and contrasting⁹⁶ so that what contributed to acceptability scores that are positive and less than positive may be identified. We will use a similar approach, content analysis, to evaluate the sustainability data.

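### The SPIRIT cost formula captures session time but not the 1½-day provider training, so on its own it understates the resources a clinic needs to replicate the intervention

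*Combined protocol and SAP*

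**What the plan says.** In Section 8.1 (Implementation Process Outcomes) the cost of the intervention is "based on the actual time the care provider spent in carrying out SPIRIT, multiplied by hourly wage", to which the plan adds benefits and materials. The measurement table in Section 3 gives the same formula for the initial and the delayed implementation: "The actual time the care provider spent in carrying out SPIRIT, multiplied by hourly wage (+benefits), plus costs of materials". The stated exclusions in Section 8.1 are "Overhead (e.g., facility) costs and research" staff time. Provider training appears neither among the inclusions nor among the exclusions.

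Section 6.4 describes how provider time is captured: the Interview Guide checklist, completed after each dyad encounter, records start and finish times. Section 8.1 then aggregates the minutes needed to complete the sessions. No section arranges to record training hours for costing.

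Section 6.2.1 sets the preparation required: "Care provider training will consist of a 1½-day, competency based program". It consists of three half-day modules, the last of which includes certification. In addition, "A 2-week practice period will be scheduled for integration of skills and exploration of additional learning needs".

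Section 9.4.3 gives the purpose of the cost figure: "Cost estimates will be used to ascertain resources needed to implement or replicate SPIRIT in the" future.

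**The concern.** The formula and its declared use do not match. A clinic adopting SPIRIT has to release a provider for training before the first dyad is seen, so that time is part of what implementation requires. A figure built from session minutes answers a narrower question: the recurring cost of delivery.

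Cost is one of the four Aim 2 process outcomes, and the synopsis says that aim exists to generate data for translation. If the session-only figure is quoted as the cost of adopting SPIRIT, planners will budget too little provider time. The shortfall per dyad is largest in small clinics, which have few dyads over which to spread the training.

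**Working it through.** The documents state no cost figure, so the check is on provider time. If the hourly wage is the same for training and delivery (an assumption), the ratio of times equals the ratio of wage costs. Materials are left out, so these are percentages of provider time and not of total cost.

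**Inputs**
- 400 dyads and 19 clusters (power table, Section 9.2).
- 21–22 dyads per cluster (Section 5.5).
- Session lengths of about 45 and 15 minutes (Section 6.1.1).
- An average of 82 minutes in earlier SPIRIT studies (Section 2.2), used as a sensitivity value.
- Training of 1.5 days (Section 6.2.1). Hours per day are not given; 7–8 is assumed, so T = 1.5 × 7 = 10.5 h to 1.5 × 8 = 12 h.
- One trained provider per cluster. This is an assumption, consistent with Section 6.3, which merges clinics served by the same SPIRIT provider.

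**Reproducing the plan's own figures**
- 400 / 19 = 21.05 dyads per cluster, which agrees with 21–22.
- 45 + 15 = 60 minutes, which agrees with the stated session total.

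**Training relative to delivery**

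Delivery hours D = n × m / 60, with n dyads per provider and m minutes per dyad. The added percentage is T / D, and the share of all provider time is T / (T + D).

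| Minutes per dyad | D (n = 21.05) | T | Added to delivery, T/D | Share of provider time | Minutes per dyad with training |
|---|---|---|---|---|---|
| 60 | 21.1 h | 10.5 h | 50% | 33% | 90 |
| 60 | 21.1 h | 12 h | 57% | 36% | 94 |
| 82 | 28.8 h | 10.5 h | 36% | 27% | 112 |
| 82 | 28.8 h | 12 h | 42% | 29% | 116 |

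**Effect of a larger caseload**

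Section 5.5 equates 427 patients with 20%, which implies a pool of 427 / 0.20 = 2,135, or 2,135 / 19 = 112.4 per cluster. The coverage levels below are assumptions, shown at 60 minutes per dyad:
- Half the pool (56.2 dyads): 10.5 / 56.2 = 19% to 12 / 56.2 = 21% added.
- The whole pool (112.4 dyads): 10.5 / 112.4 = 9% to 12 / 112.4 = 11% added.

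Training is 10% of provider time when D = 9T, that is n = 9 × T × 60 / m. This gives 94.5–108 dyads per provider at 60 minutes and 69–79 at 82 minutes, against the planned 21–22.

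Hours spent in the two-week practice period are not given and are not counted. The delayed phase has no stated dyad numbers, so its percentage cannot be computed.

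**The case against.** **Training is not excluded by name.** A reader might infer that the plan deliberately removes training from the cost. It does not: Section 8.1 names only overhead and research staff time. The wording could be stretched to cover training, but the plan records only encounter times, so following it as written gives a session-only figure.

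**Little information is lost.** Aim 2 is descriptive, no hypothesis in Section 9.1 uses cost, and the training length is published, so an adopter could add 1½ days unaided. Keeping one-time and recurring costs apart is also sound practice. This stands, and it is why the point is an addition to reporting and not a fault in the existing figure.

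**The percentage depends on the caseload.** This also stands. Spreading training over trial enrollees only gives a high figure, and routine use over a larger pool brings it down, as the working shows. The 60 minutes also covers sessions only. If the charting and nephrologist contact in Section 6.1.1 count as delivery, the percentage falls further.

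**Larger figures do not hold up.** A reader might take the 28 clusters listed by state in Section 6.3 (400 / 28 = 14.3 dyads each) and an 8-hour day to reach 12 / 14.3 = 84%. That needs both choices at once, and it departs from the 19 clusters and 21–22 dyads on which Sections 9.2 and 5.5 agree.

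**Other omitted time is a different matter.** A reader might also want trainer, repeat-orientation and booking time included. The documents do not support that as an error:
- The trainers are certified through the Study Coordination Center (Section 6.2.1) and are plausibly research staff, whom Section 8.1 expressly excludes.
- Repeat orientation is a trial fidelity step (Section 6.4).
- The Section 1.3 row "Scheduling SPIRIT Session I & II and 2-wk F/U" mixes session booking with research follow-up, and Section 5.5 lists confirmation calls as a retention measure.

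**Conclusion.** The point holds for provider training only. As written, the formula yields a session-only cost, while Section 9.4.3 uses it to judge the resources needed for implementation or replication. At the trial's planned volume, training adds about 50–57% to delivery time at 60 minutes per dyad, or 36–42% at 82 minutes. This assumes one trained provider per cluster, a 7- to 8-hour day and equal wage for training and delivery. At larger routine caseloads the addition is smaller, so no single percentage should be quoted without its caseload. The omission is by silence, and the primary and secondary effectiveness analyses are untouched. It is a cheap improvement for the sponsor to consider.

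**What to change.** In Section 8.1 and the Section 3 measurement table, report two lines:

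1. Delivery cost per dyad, exactly as now defined.
2. Start-up cost per clinic (or per cluster, where one provider serves several clinics): provider trainee hours for Modules 1–3, taken from attendance, multiplied by hourly wage plus benefits.

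Then show combined cost per dyad = line 1 + line 2 / number of dyads, at the caseload observed and at one or more higher routine caseloads. In Section 9.4.3, base the replication statement on both lines. Trainer hours may be listed as a count of hours; trainer, repeat-orientation, booking and reminder time need not enter the cost.

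The change needs new wording and training attendance records. It adds no burden for participants and leaves the existing figure intact. The downside is that the reported total cost will look less favourable.
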